#### Meta-Analysis for Estimated TLR with Bailout Stenting at 6-Months

Estimated TLR with Bailout Stenting at 6-Months							
Author, year	n	Weight	Treatment	Control	Risk Difference	Risk Ratio	Odds Ratio
Boisers et al., 2015	83	18.4%	5.3%	34.2%	-28.9% [-44.6%, -13.2%]	0.15 [0.04, 0.62]	0.10 [0.02, 0.47]
Krankenberg et al., 2015	119	26.3%	5.2%	26.0%	-20.8% [-33.5%, -8.1%]	0.20 [0.06, 0.65]	0.14 [0.03, 0.57]
Dipple et al., 2015	250	55.3%	26.5%	48.2%	-21.7% [-34.5%, -8.9%]	0.55 [0.39, 0.77]	0.39 [0.22, 0.68]
Total	452	100.0%	18.5%	37.9%	-19.4% [-27.8%, -11.0%]	0.49 [0.36, 0.67]	0.37 [0.24, 0.57]

The Breslow- Day test indicates that TLR with Bailout has no heterogeneity and thus can be combined into a meta-statistic (p-value=0.1764) (Figure below).

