	Safety: Major Adverse Events (MAE) at 30 days : unplanned amputation, total mortality or TLR at 30 days (TLR includes bail out stenting)		
DSMB	The study will be evaluated for safety after the first 60 patients enrolled. Stopping rule will be based on freedom from MAE at 30 days that is $> 78\%$ (bailout stent in the PTA control arm ranged from 7 to 20% in the randomized trial. Bailout stent is included as a MAE (part of the TLR definition). If maximum bailout stent occurs (20%), this allows a 2% amputation/death rate within 1 month before the study is stopped i.e. total events of 22%, or freedom from events of 78%).		
Secondary endpoints	1. Device Outcome: Categorized by < 50% residual stenosis following JS atherectomy alone and without additional adjunctive PTA or bail out procedures as determined by the Angiographic Core Laboratory.		
	2. Procedural Outcome: Categorized by < 30% residual stenosis following the protocol-defined treatment (JS + PTA) with provisional or bail out procedures as determined by the Angiographic Core Laboratory.		
	3. Procedural Success: Defined as $\leq 30\%$ residual diameter stenosis following JS + PTA without provisional or bailout procedures.		
	4. Target Lesion Revascularization (TLR) at 6 months (with no bailout stent included): TLR is defined as retreatment of the index lesion (extended 1 cm proximal and distal to the lesion) at 6 months. Intra-procedural bail out stenting of the index lesion is NOT considered meeting a TLR endpoint. (ITT analysis)		
	5. Target Lesion Revascularization (TLR) at 1 year: TLR is defined as retreatment of the index lesion (extended 1 cm proximal and distal to the lesion) at 1 year		
	ITT (bail out stent in the Lab is considered as TLR) ITT (bail out stent in the Lab is not considered as TLR)		
	
 
6. Target Lesion Patency at 6 months and 1 year: Defined as PSVR ≤ 2.5 at the treated site or < 50% stenosis by angiography as determined by the Angiographic Core Laboratory in the absence of TLR, amputation, and/or surgical bypass (the evaluation of patency is extended to one cm proximal and one cm distal to the target lesion)
 
		
	7. Clinically Driven Target Lesion Revascularization at 6 months and 1 year: Defined as any re-intervention or artery bypass graft surgery involving the target lesion in which the subject has a ≥ 70% diameter stenosis (Peak Systolic Velocity Ratio (PSVR) > 3.5 or on		

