Recently 3 randomized trials were presented in treating FP ISR; the EXCITE ISR trial (randomized laser + PTA vs PTA alone), the RELINE trial (randomized Viabahn stent vs PTA) and the Randomized Femoral Artery In-Stent Restenosis (FAIR) Trial.. In the GORE VIABAHN (W.L Gore and Associates, Newark, Delaware, USA) Versus Plain Old Balloon Angioplasty (PTA) for Superficial Femoral Artery (SFA) In-Stent Restenosis (RELINE) trial, Viabhan endograft stent was shown to be superior to PTA leading to significantly better patency rates at 1 year (37% versus 74.8% respectively). In the EXCImer Laser Randomized Controlled Study for Treatment of FemoropopliTEal In-Stent Restenosis (EXCITE ISR) trial, a multicenter, prospective, randomized, controlled trial conducted across 40 U.S. centers. A total of 169 ELA + PTA subjects (62.7% male; mean age  $68.5 \pm 9.8$  years) and 81 PTA patients (61.7% male; mean age  $67.8 \pm 10.3$  years) were enrolled. Mean lesion length was  $19.6 \pm 12.0$  cm versus  $19.3 \pm 11.9$  cm, and 30.5% versus 36.8% of patients exhibited total occlusion. ELA + PTA subjects demonstrated superior procedural success (93.5% vs. 82.7%; p = 0.01) with significantly fewer procedural complications. ELA + PTA and PTA subject 6month freedom from TLR was 73.5% versus 51.8% (p < 0.005), and 30-day major adverse event rates were 5.8% versus 20.5% (p < 0.001), respectively. ELA + PTA was associated with a 52% reduction in TLR (hazard ratio: 0.48; 95% confidence interval: 0.31 to 0.74). This trial showed that debulking with the laser is an important strategy to reduce TLR in treating FP ISR when compared to PTA. Finally, The Randomized Femoral Artery In-Stent Restenosis (FAIR) Trial, randomized 119 patients with superficial femoral artery in-stent restenosis to drug coated balloon (DCB) (n=62) versus PTA (n=57). Mean lesion length was 82.2±68.4 mm. and 28.6% of lesions were totally occluded. The primary end point of recurrent in-stent restenosis assessed by ultrasound at 6 months was 15.4% (8 of 52) in the DCB and 44.7% (21 of 47) in the PTA group (P=0.002). Freedom from target lesion revascularization was 96.4% versus 81.0% (P=0.0117) at 6 months and 90.8% versus 52.6% (P<0.0001) at 12 months, respectively. No major amputation was needed. Two patients in the DCB and 3 patients in the PTA group died. No death was procedure related.

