#### 5.12 Assumptions:

TLR with bailout stenting from historic control from meta-analysis:37.9%TLR with bailout stenting from Jetstream ISR feasibility study:20.7%Power 80%Alpha 0.05

We are planning a study of independent cases and controls with 1 control(s) per case. Prior data indicate that the failure rate among controls is 0.38. If the true failure rate for experimental subjects is 0.21, we will need to study 112 experimental subjects and 112 control subjects to be able to reject the null hypothesis that the failure rates for experimental and control subjects are equal with probability (power) 0.8 (meta-analysis from published randomized trials provides data on 182 controls). The Type I error probability associated with this test of this null hypothesis is 0.05. We will use an uncorrected chi-squared statistic to evaluate this null hypothesis. Assumingly a loss of 20% of patients on follow-up a minimum of 134 patients will be enrolled.

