### 5.25 ANALYSIS OF OUTCOMES

We hypothesize that JetStream atherectomy is superior to plain old balloon angioplasty in treating femoropopliteal in-stent restenosis in regards to the primary effectiveness endpoint of target lesion revascularization at 6 months with bailout stenting considered as a TLR. The Null Hypothesis assumes that the active control (JetStream) and the historic control of TLR (derived from the meta-analysis) have the same TLR at 6 months by intention to treat analysis. We calculated that if TLR is 0.38 for balloon angioplasty and 0.21 for JetStream, we need a total of 112 experimental subject and 112 control to reject the null hypothesis with a power of 0.8 and alpha of 0.05. The meta-analysis has provided data on TLR for balloon angioplasty in more than 112 controls. To account for patient loss to follow up we plan to enroll a maximum number of 140 patients in this study

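### The homogeneity test behind Appendix A's pooling concerns odds ratios, but JET-ISR borrows only the PTA event rate, and on the printed counts that rate varies from 26% to 48% between the three arms

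*Combined protocol and SAP*

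**What the plan says.** Appendix A tabulates estimated 6-month counts of TLR with bailout stenting for both arms of three randomized trials. The PTA arms are 15/44 (stent-graft trial), 15/57 (drug-coated-balloon trial) and 39/81 (laser trial), with a total of 69/182, or 37.9%. Below the treatment-versus-control table it says that "TLR with Bailout has no heterogeneity and thus can be combined into a meta-statistic (p-value=0.1764").

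Only the control column is carried forward. Section 5.12 takes 37.9%, rounded to 0.38, as the control rate and adds: "We will use an uncorrected chi-squared statistic to evaluate this null hypothesis". The null in section 5.25 is that JetStream and "the historic control of TLR (derived from the meta-analysis) have the same TLR at 6 months". The same section words its hypothesis more widely: "JetStream atherectomy is superior to plain old balloon angioplasty in treating femoropopliteal in-stent restenosis".

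Section 5.12 computes 112 against 112 and notes that 182 controls are available. It does not say how many enter the test. Section 5.12 sets alpha at 0.05. The closing part of Appendix A prints 0.025 in its list of assumptions and 0.05 in the paragraph below it.

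**The concern.** Odds ratios can agree across trials while the control rates differ widely, and the reverse is also possible. A non-significant Breslow-Day test therefore says nothing about whether three PTA arms share one event rate. It is the only statement on homogeneity in the supplied text, and the quantity being pooled is the comparator for the primary effectiveness test.

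What is at stake is the reach of the conclusion. If the arms differ, the JetStream result needed for superiority depends on which historical trials happen to be in the pool. A significant result would then support superiority to these three arms as summed. It would not by itself support superiority to PTA in general.

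A second question is whether the three counts measure the same thing. Section 3.2 reports for the laser trial that 6-month "freedom from TLR was 73.5% versus 51.8"%, so its PTA arm had 48.2% TLR. This is the same as Appendix A's figure for TLR with bailout. For the drug-coated-balloon trial section 3.2 reports: "Freedom from target lesion revascularization was 96.4% versus 81.0% (P=0.0117) at 6 months". That is 19.0% TLR in the PTA arm, against 26.0% in Appendix A. The synopsis says that "bailout stent in the PTA control arm ranged from 7 to 20% in the randomized trial". So a bailout allowance is visible in one arm and not in the other.

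**Working it through.** **Inputs.** PTA counts 15/44, 15/57 and 39/81 (Appendix A); rates 0.38 and 0.21, power 0.8, alpha 0.05, uncorrected chi-squared (section 5.12).

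**1. The plan's own figure.** With mean rate 0.295, n per group = [1.960·√(2·0.295·0.705) + 0.842·√(0.21·0.79 + 0.38·0.62)]² / 0.17² = 111.8, so 112. This reproduces the plan at two-sided 0.05, which is the same as one-sided 0.025. Two-sided 0.025 would need 136 per group. With all 182 controls, power at 0.21 versus 0.38 is about 88%.

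**2. The 37.9%.** (15 + 15 + 39)/(44 + 57 + 81) = 69/182 = 37.9%. It is a raw sum.

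**3. Homogeneity of the PTA rates.** The rates are 34.1%, 26.3% and 48.1%. Expected events at 69/182 are 16.68, 21.61 and 30.71; expected non-events are 27.32, 35.39 and 50.29. Summing (observed − expected)²/expected over both columns:
- stent-graft trial: 0.17 + 0.10
- drug-coated-balloon trial: 2.02 + 1.23
- laser trial: 2.24 + 1.37

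The total is 7.13 on 2 df, p = 0.028. Because the counts are estimates, each arm was shifted by −1, 0 or +1 event. Over the 27 combinations p runs from 0.008 to 0.077, and 23 are below 0.05.

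**4. The superiority limit.** This is the largest x of 112 with p ≤ 0.05, where z = (e/m − x/112)/√[p̄(1 − p̄)(1/112 + 1/m)], p̄ = (x + e)/(112 + m), and e/m is the control count.

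| Controls | Rate | Limit, two-sided 0.05 | p at limit | Limit, two-sided 0.025 |
|---|---|---|---|---|
| All, 69/182 | 37.9% | 30 | 0.04995 | 28 |
| Without laser, 30/101 | 29.7% | 20 | 0.042 | 18 |
| Without drug-coated balloon, 54/125 | 43.2% | 34 | 0.041 | 32 |
| Without stent graft, 54/138 | 39.1% | 30 | 0.040 | 28 |

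Part of the fall from 30 to 20 is lost sample: 101 controls at almost the same rate (38/101 = 37.6%) already give a limit of 28.

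**5. At the planned JetStream rate.** A rate of 21% is 23 to 24 failures of 112. Then p is 0.002 to 0.003 against all arms and 0.12 to 0.17 without the laser arm. With the historical counts held as printed, the binomial chance of meeting the limit is 94% for 30/112 and 25% for 20/112.

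**6. Level of the planned test for the stated null.** Hold the three arms' true rates at 15/44, 15/57 and 39/81, set the JetStream true rate to 69/182, and let all counts vary binomially. The exact type I error is 4.9% two-sided, 2.4% in favour of JetStream.

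**7. Random-effects control rate.** DerSimonian-Laird on the logit scale gives Q = 6.98, between-trial SD 0.44 and a pooled rate of 36.4% (95% CI about 24% to 51%). Three trials barely identify the SD: its Q-profile interval is 0 to 3.0.

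**The case against.** Much can be said for the plan. Section 5.25 defines its null against the historic control from this meta-analysis, and step 6 shows that the chi-squared test holds its level for that null. A reader might infer that the primary test has an inflated error rate. The documents do not support this: inflation arises only for the wider claim, and its size would depend on a between-trial SD that they do not give.

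A reader might also infer that 20/112 is the proper limit, or that the plan is biased towards the device. Neither follows. Only one of the three exclusions lowers the limit; another raises it to 34. The laser arm is the largest (81 of 182). Its mean lesion length of 19.3 cm is also closer to the feasibility study's 17.4 cm than the drug-coated-balloon trial's 8.2 cm is. If JET-ISR enrols long lesions, 37.9% may be too low as a comparator and count against the device.

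The heterogeneity is not firmly established. The counts are estimates, p can exceed 0.05 after one-event shifts, and only the 26% versus 48% contrast is individually below 0.05 (p = 0.010).

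Finally, a reader might infer that bailout was left out of the laser arm. The documents do not show this. That trial's TLR may already include bailout, and the 7 to 20% range is not assigned to particular arms.

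It could be added that the Breslow-Day sentence speaks only of a combined meta-statistic. But no other justification for combining the trials is given, and the combined control rate is what the trial uses. That part of the point stands.

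**Conclusion.** The stated reason for pooling does not bear on the quantity pooled. On the printed counts the relevant check points the other way (p = 0.028; 0.008 to 0.077 under one-event shifts). The limit for superiority is 30 of 112 with all arms and 20, 34 or 30 when one arm is left out. These limits assume 112 evaluable JetStream subjects, two-sided alpha 0.05 and the estimated counts as printed.

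The primary test stands for equality with this pooled control. What is not supported is reading a significant result as superiority to PTA in general, because that reading ignores variation between the historical trials. The direction of any bias is unknown. Whether all three counts include bailout cannot be settled from the documents. The point should be fixed, but it does not invalidate the design.

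**What to change.** 1. **Appendix A.** Stop citing Breslow-Day as the reason for pooling. Describe 37.9% as the raw sum 69/182. Report the homogeneity of the three control rates, with the caveat that the counts are estimated. Show for each arm how TLR and bailout were combined, and reconcile the result with section 3.2 (48.2% in both places for the laser trial; 26.0% against 19.0% for the drug-coated-balloon trial). Reconcile the two printed alpha values.
2. **Sections 5.12 and 5.25.** State that all 182 controls enter. Keep the uncorrected chi-squared test as primary. Word its conclusion as superiority to this pooled historic control.
3. **Before outcomes are seen.** Prespecify all three leave-one-out comparisons and the random-effects control rate as descriptive sensitivity analyses, reported together and not decisive.

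The cost is some wording, a little analysis and a more cautious general claim; the primary test, sample size and power do not change. At a true JetStream rate of 21% and with the control counts as printed, the limit without the laser arm is met only about 25% of the time, so disagreement with the primary result is likely. That is a reason to keep these analyses descriptive. A simulation with truly equal PTA rates of 37.9% and a JetStream rate of 21% found that requiring every leave-one-out pool to agree would qualify about 22% of primary successes. None of these analyses removes case-mix differences between JET-ISR and the historical trials.

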#### New Statistical analysis for Jet-ISR

TLR with bailout stenting from historic control from meta-analysis:37.9%TLR with bailout stenting from Jetstream ISR feasibility study:20.7%(2 bailout stent for suboptimal results + 4 TLR at 6 months/29 limbs)20.7%Power 80%Alpha 0.025

If one assumes a 1:1 ratio of actual treatment: control (instead of the original 2:1)

We are planning a study of independent cases and controls with 1 control(s) per case. Prior data indicate that the failure rate among controls is 0.38. If the true failure rate for experimental subjects is 0.21, we will need to study 112 experimental subjects and 112 control subjects to be able to reject the null hypothesis that the failure rates for experimental and control subjects are equal with probability (power) 0.8 (meta-analysis provides 182 controls which is more than needed for this analysis). The Type I error probability associated with this test of this null hypothesis is 0.05. We will use an uncorrected chi-squared statistic to evaluate this null hypothesis. Assumingly a loss of 20% of patients on follow-up a minimum of 134 patients will be enrolled.

# Supported by

**Boston Scientific** 

Changes include:

Page 27: Section 4.4.2 Exclusion Criteria 20 is changed from "Stents not fully apposed to vessel wall or overlapping stent segments" to "stents unapposed to either vessel wall or unapposed to overlapping stent segments. Apposed overlapping stents is not an exclusion"

Page 29: Section 4.47 Blinding consists of correction of a grammatical error from "arms" to "arm"

Page 29: Section 4.44 General Exclusion Criteria 9 is changed from "Has a history of gastrointestinal bleeding in the past 1 month prior to index procedure, or any history of hemorrhagic diathesis" to "Has a history of gastrointestinal bleeding in the past 3 months prior to index procedure, or any history of hemorrhagic diathesis."

Page 30: Table 1 Study Assessment of Hemoglobin A1C is completely removed

Page 30: Table 1 Study Assessment Creatinine draw time Pre-Discharge is changed from 72 hours post procedure +/- 24 hours to 72 hours post procedure +/- 48 hours

Page 30: Table 1 Study Assessment Duplex Ultrasound Pre-Discharge is changed from "The first duplex ultrasound can occur any time within 45 days after the index procedure" to "The first duplex ultrasound is optional and can occur any time within 45 after the index procedure."

#### Page 30: Section 4.52 Creatinine

"Creatinine will be obtained and documented at baseline, 72 hours post procedure (+/-) 24 hours, and at 1 year follow-up visit" is change to "Creatinine will be obtained and documented at baseline, 72 hours post procedure (+/-) 48 hours, and at 1 year follow up visit."

Page 31: Section 4.53 will be completely removed.

#### Page 31: Section 4.58 Duplex Ultrasound

Second sentence will be changed from "DUS is required within 45 days of the index procedure (at either the pre-discharge or 30-Day visit), at 6 months, and at 1 year post-procedure" to "DUS is optional within 45 days of the index procedure (at either the pre-discharge or 30-Day visit), and required at 6 months, and at 1 year post-procedure."

#### Page 35/36: Table 3: Pre-Discharge Assessment Requirements

Duplex Ultrasound\* "First duplex ultrasound can occur any time within 45 days of the procedure" will be change to Duplex Ultrasound\* "First duplex ultrasound is optional and can occur any time within 45 days of the procedure."

Page 35: Table 3: Pre-Discharge Assessment Requirements will have the addition of "Creatinine will be obtained and documented at baseline, 72 hours post procedure (+/-) 48 hours, and at 1 year follow up visit."
